10.4 Laboratory Evaluations

Laboratory parameters that can be graded using CTCAE will be graded and the following subject incidence summaries will be produced:

This document is confidential.

- Worst post-Baseline severity grade
- Shift summary of Baseline grade to worst post-Baseline severity grade

Line plots selected laboratory parameter values will be produced by plotting actual values against the sample collection study day for individual subjects in Pooled Placebo, and each EQ001 Dose Group.

A by-subject listing will also be created. In all laboratory data summaries and listings results reported in SI units will be used.

10.5 Pregnancy

Pregnancy testing in women of childbearing potential (WOCBP) will be obtained with a urine and serum beta human chorionic gonadotropin test (β HCG). A pregnancy test will be performed during Screening, Day 1, Day 57, and at Day 85 visit.

Pregnancy test results, including the type of pregnancy test performed at visit will be presented in a by-subject listing.

10.6 Vital Signs

Vital signs will include systolic and diastolic blood pressures (mmHg), pulse rate (beats/min), respiratory rate (breaths/min), temperature ($^{\circ}$ C or $^{\circ}$ F) and weight (kg).

Temperature collected in $^{\circ}$ F will be converted into $^{\circ}$ C using the following formula:

$$\text{Temperature } ({}^{\circ}\text{C}) = [\text{Temperature } ({}^{\circ}\text{F}) - 32] \times (5/9)$$

The actual and change from Baseline values of vital signs will be summarized by visit presented in a table, using continuous descriptive summary statistics at Baseline and each post-Baseline visit. In addition, number and percent of subjects with out of range vital signs at any post-baseline visit will also be summarized for the following categories:

Blood Pressure:

- SBP > 150 mmHg or DBP > 100 mmHg
- SBP < 90 mmHg or DBP < 60 mmHg

Heart Rate:

- < 50 beats per min
- > 120 beats per minute
- \geq 30 beats per minute increase from baseline
- \geq 30 beats per minute decrease from baseline

Respiratory Rate:

- < 8 breaths per minute
- > 20 breaths per minute

A by-subject listing will also be created. Vital signs will be collected pre-dose and 30 minutes after the injection at each dosing visit and will be listed in a by-subject listing.

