Study Day 1 (Baseline) assessments will include the following: a targeted physical examination, vital signs, laboratory tests, anti-EQ001 antibody test, AE and ACQ-6 monitoring, recording concomitant medications, [REDACTED] pulmonary function testing, and measurement of fractional exhaled nitric oxide (FeNO). If appropriate, repeat assessments can be performed within the Screening Period with approval from the Medical Monitor, as needed.

EQ001 or placebo doses will be administered in the clinic; [REDACTED]

All subjects will undergo the following procedures at every visit except Day 4 (Screening; Study Day 1 [Baseline]; and Study Days 8, 15, 29, 43, 57, and 85): Complete (Screening) or interval (all other study days) medical and surgical histories; complete (Screening) or targeted (all other study days) physical examination; vital signs; hematology and serum chemistry laboratory tests; pulmonary function test; FeNO; AE monitoring (including assessments for injection site-related and hypersensitivity reactions); ACQ-6; and recording of concomitant medications and treatments. EQ001 serum levels will be measured at every visit except Screening.

[REDACTED] . [REDACTED]

[REDACTED]

Pregnancy testing for women of childbearing potential (WOCBP) will be assessed at Screening, Study Day 1 (Baseline), and on Study Days 57 and 85. Electrocardiograms will be performed at Screening, Baseline, and on Study Days 8, 57, and 85.

Early Termination or Unscheduled Visit:

Subjects who receive ≥ 1 dose of study drug should be encouraged to complete all study visits. If subjects do not complete all study visits, or terminate early from the study, they will be asked to return to the study site for an Early Termination (ET) Visit within 28 days of the last dose of study drug administration. [REDACTED]

[REDACTED]

[REDACTED]

[REDACTED] In addition, if at any time up to Study Day 85 (or ET) a subject has an unscheduled study visit, all procedures that were conducted at that visit will be collected in the electronic case report form (eCRF) as an unscheduled visit.

[REDACTED]

[REDACTED]

[REDACTED]

[REDACTED]

[REDACTED]
[REDACTED]
[REDACTED]
[REDACTED]
Study drug should be administered so that there are at least 12 days between doses.

Data Review Committee, Dose-Limiting Toxicity, and Stopping Criteria:

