6 STUDY ENDPOINTS

6.1 Primary Endpoints

Safety and tolerability of EQ001, as assessed by treatment-emergent adverse events (TEAEs), treatment-emergent serious adverse events (TESAEs), clinical laboratory values, ECGs, vital signs, and physical examinations

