10.4 Vital Signs

The following vital sign measurements will be performed: systolic (SBP) and diastolic blood pressure (DBP), pulse, respiration rate, and temperature. On dosing days, vital signs will be taken pre-dose. Vital signs (except for temperature) will also be periodically monitored for a minimum of 30 minutes following the SC administration of study drug. The subject must be seated or in a semi-recumbent position in a rested, calm state for at least 3 minutes before vital signs are collected. The position selected for a subject should be the same throughout the study and documented on the vital signs eCRF.

Height will be measured without shoes at Screening.

Weight without shoes will be obtained at Screening. On dosing days, weight will be obtained before dosing. The weight at Screening will be used to calculate all study drug doses, unless there has been a weight change of $\geq 20\%$ from Screening.

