6.2 Key Definitions

- **Relative study day:** A relative study day is a day of any study assessment relative to the first dose of study drug. The day of the first dose of the study drug will be considered as Day 1 (Visit Day 1 per protocol). Pre-treatment and on-treatment study days are numbered relative to the day of the first dose of study drug. The preceding day of the first dose of the study drug will be considered as Day -1 and next day after the first dose of the study drug will be considered as Day 2 and so on. There will not be a study day of Day 0.
- **Baseline Value:** Unless indicated otherwise, baseline value of a variable is defined as the last non-missing value on or prior to the first dose of study drug. If there are two values qualifying for the baseline value (e.g., FeNO measurements are taken in duplicate), the average of the two will be considered as the baseline value.

This document is confidential.

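### As worded, the SAP's post-baseline vital-sign tables leave out the readings taken after the first injection and do not say which reading is used on later dosing days

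*SAP*

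**What the plan says.** Protocol 6.1 makes vital signs part of the primary endpoint, which besides TEAEs and TESAEs covers "clinical laboratory values, ECGs, vital signs, and physical examinations". Protocol 10.4 has vital signs taken before each dose; apart from temperature, they "will also be periodically monitored for a minimum of 30 minutes following the SC administration of study drug".

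SAP 10.6 then plans three outputs:

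- Actual values and changes from baseline, "summarized by visit presented in a table, using continuous descriptive summary statistics at Baseline and each post-Baseline visit".
- The "number and percent of subjects with out of range vital signs at any post-baseline visit", with limits for blood pressure, heart rate and respiratory rate.
- A listing: "Vital signs will be collected pre-dose and 30 minutes after the injection at each dosing visit and will be listed in a by-subject listing".

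Two definitions bear on these outputs. The Protocol synopsis (2.1) identifies the first dosing day with Baseline: "Study Day 1 (Baseline) assessments will include the following: a targeted physical examination, vital signs". SAP 6.2 states that the "baseline value of a variable is defined as the last non-missing value on or prior to the first dose of study drug", and averages the values if two qualify. Protocol 13.1 is stricter: the baseline value must come before any study drug is received.

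**The concern.** The readings after an injection are the ones best placed to show an acute effect on blood pressure, pulse or respiration. Protocol 4.6 describes this as the first study of repeated subcutaneous dosing, so the first injection is of particular interest. Both vital-sign tables are worded by visit, and the visit of the first injection is the Baseline visit. Programmed as written, the tables would give no post-baseline row or count to what happened after dose 1.

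The later dosing days have a different problem. Each has a pre-dose and a 30-minute reading, and the visible text has no rule for choosing between them. Pre-dose values on Days 15 to 57 describe the subject about 14 days after the previous dose. Mixing the two readings would dilute an acute effect. Two competent programmers could produce different tables for a component of the primary endpoint.

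**Working it through.** **1. Enrolment, to fix the denominators.** Each cohort has 8 subjects at 3:1, so 8 × 3/4 = 6 active and 2 placebo. Four cohorts give 4 × 8 = 32. The repeated cohort gives 32 + 8 = 40 in total, with 6 + 6 = 12 at the MTD, 4 × 2 + 2 = 10 on placebo and 4 × 6 + 6 = 30 active. All of these match the documents.

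**2. Post-injection sets.** Doses fall on Days 1, 15, 29, 43 and 57 (Protocol 2.1), so there are 5 per subject. The count assumes that every dose is given and that one 30-minute set follows each.

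| Subjects | All sets | Day 1 sets | Days 15–57 sets |
|---|---|---|---|
| 32 | 32 × 5 = 160 | 32 | 32 × 4 = 128 |
| 40 | 40 × 5 = 200 | 40 | 40 × 4 = 160 |

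Day 1 accounts for 1/5 = 20% in either case.

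**3. Where each reading goes when SAP 10.6 is read literally.**

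| Reading | By-visit table | Out-of-range count | Listing |
|---|---|---|---|
| Day 1 pre-dose | Baseline row | Not applicable | Yes |
| Day 1, 30 minutes | No post-baseline row | Not counted | Yes |
| Days 15–57 pre-dose | Not settled | Counted | Yes |
| Days 15–57, 30 minutes | Not settled | Can be counted; not stated | Yes |
| Days 8 and 85 (no injection) | Yes | Counted | Yes |

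Every parameter with an out-of-range limit in SAP 10.6 is one that Protocol 10.4 monitors after injection; temperature, the exception, has no limit. Neighbouring SAP sections are worded differently. Section 10.4 takes the worst post-baseline laboratory grade and 10.7 the worst QTcF increase after baseline, and neither ties these to a visit.

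**4. Baseline.** Let the Day 1 pre-dose pulse be P and the 30-minute pulse P + d, and take d = 30, the SAP's own heart-rate change limit.

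| Baseline rule | Baseline | Change at Day 1, 30 minutes | Change at a later reading of P |
|---|---|---|---|
| Last value before injection, by clock | P | +30 | 0 |
| Last value on the date of first dose | P + 30 | 0 | −30 |
| Average of the two Day 1 values | P + 15 | +15 | −15 |

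Under either date-based rule the rise would fall below the limit even if the reading were tabulated. Under the second, a return to normal would be flagged as a decrease. The SAP does not say that baseline is assigned by date, but no clock-time rule is visible.

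**5. Weight of one subject.** With 6 active subjects in a cohort, one uncounted subject moves an incidence by 1/6 = 17 percentage points. In a repeated MTD cohort it is 1/12 = 8 points, and in the pooled active group of 30 it is 1/30 = 3 points.

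There is no hypothesis test (SAP 6.1), so no error rate or power figure is affected.

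**The case against.** The strongest reply is that SAP 10.6 excludes nothing. The listing sentence covers pre-dose and post-dose readings together. If being listed meant being listed only, the pre-dose values would also be barred from the by-visit table in the same section, which cannot be intended. The SAP promises listings for nearly every data type, usually alongside tables. A reader might infer that all 160 (or 200) post-injection sets are confined to a listing, but the text does not support that. Days 15, 29, 43 and 57 are post-baseline visits, and nothing limits the out-of-range count there to pre-dose values. A programmer might also treat any reading after the baseline value as post-baseline, which would bring in Day 1.

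A reader might further infer that the primary safety tables as a whole can miss acute reactions to the first dose. That also goes too far. Subjects are observed for at least 30 minutes (Protocol 9.3). Adverse-event monitoring covers injection-site and hypersensitivity reactions, and the DLT definition includes reactions of Grade 3 or higher (Protocol 2.1). TEAEs count from dosing and are tabulated, as are DLTs (SAP 10.3). The Data Review Committee sees all available safety data.

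These points narrow the concern without removing it. The literal gap for Day 1 remains, as does the missing time point on later dosing days. The adverse-event route depends on an investigator judging the value to be an event. Protocol 10.3 and 10.10 say that clinically significant examination and ECG findings are recorded as adverse events, while the visible text of Protocol 10.4 has no matching sentence for vital signs. An out-of-range table is the check that does not depend on that judgement.

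**Conclusion.** The point holds in a limited form. Followed literally, SAP 10.6 leaves up to 32 of 160 scheduled post-injection sets (40 of 200 with the repeated cohort) out of the post-baseline vital-sign tables, all of them after the first dose. The other 128 (or 160) are undetermined, not excluded. What could go untabulated is a transient out-of-range value after dose 1 that is not recorded as an adverse event; it would still be in the listing.

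The counts assume planned cohort sizes, all five doses and one set per dose. Protocol 10.4 describes periodic monitoring, so more than one set may exist, and a cohort may enrol up to 10 subjects to reach 8 evaluable for DLT. The Schedule of Events, Protocol Section 12 and SAP 6.3 are not visible, and a time-point rule there would resolve part of this. Because the ambiguity can change counts for a primary-endpoint component, it should be settled before database lock.

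**What to change.** Amend SAP 10.6 in three places:

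1. Define the out-of-range table over all readings after the first injection, including the Day 1 post-dose and unscheduled readings. SAP 6.1 keeps unscheduled data out of by-visit tables unless otherwise specified, so the inclusion has to be written down.
2. Take vital-sign baseline as the last reading before the first injection by clock time, in line with Protocol 13.1.
3. Use pre-dose values in the by-visit table, and add a table of change from same-day pre-dose to 30 minutes post-dose by dose number and treatment group. Temperature drops out because it is not part of the post-dose monitoring.

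The data are already collected. The cost is one more descriptive table with small groups, and slightly higher out-of-range counts because more readings are eligible.

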10.7 Electrocardiogram (ECG)

A standard 12-lead ECG will be performed at Screening, Day 1, Day 8, Day 57 and Day 85. The subjects will be in a seated, semi-recumbent, or supine position in a rested, calm state for at least 10 minutes before ECG assessment is performed. Any clinically significant abnormal ECG findings will be recorded as an AE.

The actual and change from Baseline values of ECG parameters will be summarized by visit presented in a table, using continuous descriptive summary statistics at Baseline and each post-Baseline visit.

The number and percentage of subjects with worst (highest) increase in QTcF from baseline to post-baseline will be summarized for the following categorical increases:

- ≤ 0 ms
- $> 0-\leq 30$ ms
- $> 30-\leq 60$ ms
- > 60 ms

The frequency and percentage of overall interpretation of ECGs will also be summarized by visit.

A by-subject listing will also be created.

10.8 Physical Examination

A complete physical examination will be done at Screening. A targeted physical exam will be done at all other scheduled visits except Day 4. All clinically significant abnormalities will be recorded either as medical history or adverse event based on the occurrence of the abnormality prior to or after the Baseline visit.

Physical examination findings prior to the first dose of study drug administration will be recorded on the medical history eCRF; clinically significant findings after the first study drug dose will be recorded as AEs.

At a minimum, the complete physical examination will include assessments of the skin, head and neck, lungs, cardiovascular (CV) system, abdomen, thyroid, and extremities. A targeted physical examination will include assessment of the lungs and any new subject complaints or changes from baseline.

A by-subject listing will be created for physical examination data.

[REDACTED]

[REDACTED]

This document is confidential.

[REDACTED]

12 Changes from Analysis Planned in Protocol

There are no changes from the analyses planned in the protocol.

This document is confidential.

This document is confidential.
